# Synopsis

## Primary Objective

The primary objective of this randomized crossover study is to determine whether a very low carbohydrate diet improves glycemic changes (measured by continuous glucose monitors) when compared to a standard carbohydrate diet in youth with type 1 diabetes.

## Secondary Objective (if applicable)

The secondary objectives of the study are to compare metabolic responses (epinephrine, glucagon, cortisol) to hypoglycemia when youth with type 1 diabetes follow a low carbohydrate versus standard carbohydrate diet using the 2-step hyperinsulinemic euglycemic-hypoglycemic clamp and stable isotope infusions. The euglycemic portion of the clamp will allow us to determine the hepatic and peripheral insulin sensitivity changes after 2 weeks on each diet.

## Study Duration

4 years

## Study Design

This is a prospective randomized crossover study of youth with type 1 diabetes.

## Number of Study Sites

Yale New Haven Hospital, Hospital Research Unit (HRU), Church Street Research Unit (CSR), Masonicare, and the Pediatric Diabetes Research Center at [name].

## Study Population

This study will enroll 20 participants with type 1 diabetes between the ages of 12 and <25 years of age from any racial or ethnic group. Participants will be recruited from the Pediatric and Adult Diabetes Clinics at Yale or those in the community capable of traveling to Yale for study procedures.

## Number of Participants

20

## Primary Outcome Variables

### Aim 1:

Primary Efficacy Outcome: Percent time spent in the target range of 70-180 mg/dL during 2 weeks on each diet.

Secondary Safety Outcomes: We will measure the percent time spent in the hypoglycemic (<54 mg/dL, <70 mg/dL) and hyperglycemic (>180 mg/dL, >250 mg/dL) ranges. We will also measure the average sensor glucose values, standard deviation, and coefficient of variation during each 2-week diet period. We will compare the proportion of days with elevated fasting beta-hydroxybutyrate levels ( $\geq 0.6$  mmol/L) during each diet period. Number of episodes of diabetic ketoacidosis and severe hypoglycemic events during each period (baseline, diet periods, and washout period) will also be reported.

## Secondary and Exploratory Outcome Variables (if applicable)

### Aim 2:

Primary Safety Outcomes: Mean levels of glucagon produced in response to hypoglycemia after each diet will be measured using a 2-step hyperinsulinemic euglycemic-hypoglycemic clamp. These will be measured after 15, 30, 45, and 60 minutes of euglycemia and hypoglycemia.

Secondary Safety Outcomes: Measurements of mean levels of other counterregulatory hormones (cortisol, epinephrine, norepinephrine), beta-hydroxybutyrate that are produced in response to hypoglycemia during the clamp will be compared after each diet period during the clamp procedures. Additionally, fasting levels of glucagon, free fatty acids, beta-hydroxybutyrate and IGF-1 (measure of growth hormone secretion) prior to the clamp will be compared after each diet period.

Secondary Efficacy Outcomes: Hepatic glucose production and adipose tissue lipolysis will be measured using stable isotope infusions during the euglycemic and

hypoglycemic portions of the clamp. We will compare differences in hepatic glucose production during each clamp between a standard and very low carbohydrate diet. We will also measure glycogenolysis and gluconeogenesis using deuterated water.

**Aim 3:**

Primary Safety Outcome: We will measure hypoglycemia awareness symptoms after 20-30 minutes of euglycemia and hypoglycemia during each clamp using a validated Edinburgh Hypoglycemia Symptom questionnaire. Scores during euglycemia will be compared to scores during hypoglycemia for each clamp. Scores during hypoglycemia after each diet period will also be compared.

Primary Efficacy Outcome: To describe how participants feel about and react to following a very low carbohydrate diet, interviews will be conducted over zoom (HIPAA compliant). Data will be coded and emerging patterns will be combined into descriptive themes.

## Abbreviations

Abbreviation	Explanation
T1D	Type 1 diabetes
VLCD	Very low carbohydrate diet
HRU	Hospital Research Unit
CSRU	Church Street Research Unit

# 1 Introduction

**1.1 Introductory Statement:** As more adolescents with type 1 diabetes (T1D) opt to follow very low carbohydrate diets to improve glucose control, it is becoming increasingly important to study the metabolic and neurological changes that occur on these diets and how these effect patient safety. Understanding the impact of dietary changes on metabolic and neurological factors will help guide clinical advice about the overall safety and efficacy of these diets in the pediatric T1D population. This work will be the basis of future studies testing dietary interventions to improve glycemic control and ensure that these dietary interventions are safe for growing youth with T1D.

## 2 Background

### 2.1.1 Preclinical Experience

Data from the Diabetes Control and Complications Trial (DCCT) demonstrated that lowering the A1c by intensive insulin management to near-normal glycemic levels decreases the risk of complications related to diabetes (1). However, intensive management in the DCCT was accompanied by marked increases in severe hypoglycemia and more recent data have implicated increased insulin doses as risk factors for cardiovascular disease in T1D 7. One approach to achieve targeted glycemic control with less insulin exposure is through the use of a very low carbohydrate diet (VLCD), defined as limiting carbohydrate intake to 50 grams per day or less 8. In adults with T1D, these diets have been shown to achieve exceptional glycemic control with physiologically normal A1c values with lower total daily insulin doses due to decreased mealtime insulin for low amounts of carbohydrate intake. (9,10)

In this study, we plan to look at very low carbohydrate diets, composed of less than 15% of calories from carbohydrates, or about 75 grams of carbohydrates per day and compare them to standard carbohydrate diets composed of at least 40% of calories from carbohydrates, or about 200 grams of carbohydrates per day. In clinical practice, both of these levels of carbohydrate intake are feasible to maintain long-term, and thus were chosen for this study.

### 2.2 Background/prevalence of research topic

As recently reported by the Type 1 Diabetes Exchange (T1DX) Registry, adolescents with type 1 diabetes (T1D) was the age group that had the highest hemoglobin A1c (A1c) levels compared to older participants; young adults aged 10-25 years were a close second (1). While the American Diabetes Association (ADA) previously recommended youth target A1c of <7.5% and adults <7%, only 17% of youth and 21% of young adults in the T1DX achieved these targets despite increased penetrance of diabetes technologies into clinical care (2,3). More recently, the target A1c level was lowered for adolescents to 7% (4). These

data suggest a need for novel approaches to improve glycemic control in adolescents and young adults with T1D.

Even for youth who are engaged in actively managing T1D, postprandial hyperglycemia continues to pose a challenge for many reasons, including, delayed insulin absorption and action compared to absorption of glucose from the gastrointestinal tract and dysregulated glucagon secretion after mixed meals (5). Moreover, postprandial glycemic changes can differ substantially depending on the macronutrient composition of the meal. Specifically, meals with reduced carbohydrate but increased fat and protein content will lessen immediate postprandial hyperglycemia (6). For many, being able to avoid carbohydrates and adhere to a very low carbohydrate diet may be easier than administering varying amounts of insulin for variable amounts of carbohydrate intake. Importantly, VLCDs have not been formally studied in adolescents and young adults with T1D. Observational data on children using a VLCD are also conflicting. A small case series of 6 children with T1D on a low carbohydrate diet showed deficits in anthropomorphic measurements and elevated lipids, though in some cases a caloric deficit was also reported(7). Conversely, a recent observational study of 131 children with T1D on a VLCD reported no significant change in height percentile or SDS after initiating the diet (8). Prior studies have explored use of low carbohydrate diets in T1D, but none have specifically monitored for ketosis. In those studies, it is likely that the lack of carbohydrate intake led to lower insulin needs, thus increasing lipolysis and ketogenesis, and levels of ketosis while on this type of diet (9). Thus, this study aims to evaluate the metabolic and neurological effects of hypoglycemia as they relate to the diet, which is a key concern from clinicians managing patients on this diet.

### 3 Rationale/Significance

**3.1 Problem Statement:** Youth with type 1 diabetes struggle to attain healthy glucose targets despite advances in diabetes technology. Adjunctive therapies to optimize glycemic control have not shown any benefit for youth with type 1 diabetes (10). Observational data in adults with T1D suggest that a very low carbohydrate diets reduce both hyperglycemia and hypoglycemia (8). However, the efficacy (time in target range) and safety of short-term use of very low carbohydrate diets in adolescents with diabetes has not been established.

**3.2 Purpose of Study/Potential Impact:** Very low carbohydrate diets have not been prospectively studied in adolescents and young adults with T1D. The participants in this study are likely to experience improvement in their blood glucose management when following a very low carbohydrate diet. This study will help guide treatment decisions, safety considerations, and dietary recommendations for national and international diabetes associations. The studies carried out in this proposal will provide important safety and efficacy information about very low carbohydrate diets in adolescents with T1D and have the potential to change the current standards of care.

**3.2.1 Potential Risks**

- **Hypoglycemia/hyperglycemia (hyperinsulinemic euglycemic-hypoglycemic clamp):** Hypoglycemia and hyperglycemia are risks of the hyperinsulinemic clamp procedures. During each clamp, IV insulin is infused which can cause hypoglycemia. To protect against unanticipated hypoglycemia, blood glucose levels are measured by a reliable device (YSI 2300) frequently throughout the study. Dextrose infusion will be adjusted through the IV to ensure the glucose remains at the target level. Hypoglycemia will occur during this study as this is a part of the clamp procedure. Our pediatric diabetes team is very experienced in conducting these studies; [name] will work with [name] and [name] to fine-tune her clamp skills. To prevent severe hypoglycemia, glucose levels will be monitored frequently and dextrose infusions can be adjusted immediately.
- **Stable Isotopes:** Non-radioactive stable isotope infusions will be performed during this study. Despite the theoretical risk of infection with an infusion of stable isotopes, our team has been using isotopes during clamp studies for over 17 years in children and adolescents and have not experienced any adverse events (Appendix 1).
- **Risk of indwelling catheter:** Intravenous catheters pose a potential risk of hematoma, thrombophlebitis, bleeding at the catheter insertion site, and rarely, infection.
- **Risk of anemia:** There is a risk of anemia in any study with frequent blood draws. We have calculated the amount of blood needed for the clamp procedures and will not exceed volume limits.
- **Risk of Indirect Calorimetry:** The air under the hood may become warm and stuffy, which some subjects find uncomfortable. Rarely, subjects may feel nauseated and/or claustrophobic while under the hood.
- **Risks of the Very Low Carbohydrate Diet:** Previous studies have suggested that switching to a very low carbohydrate diet can cause symptoms including nausea, vomiting, abdominal pain, constipation, fatigue, and lightheadedness. These symptoms will be screened for at follow up visits throughout the study. Continuous Glucose Monitors will be worn by all participants during the study to alert participants of hypoglycemia and hyperglycemia. Participants will be instructed to reach out to research staff if they are having issues with hyperglycemia and hypoglycemia. At each visit, participants will receive guidance on glucose monitoring, food intake, and treatment of hypoglycemia.

- **Risks of ketosis:** Risks of the very low carbohydrate diet include the development of elevated ketone levels. These will be monitored frequently in the outpatient setting and all supplies will be provided to participants. Participants will also be educated on warning signs of DKA and will be instructed to call the study team for any elevated ketone levels  $> 1$  mmol/L or if they have symptoms of ketosis (nausea, vomiting, headache). If a participant develops DKA, they will be withdrawn from the study. Hyperglycemic events will be classified as diabetic ketoacidosis (DKA) if all of the following are present:
  - Symptoms of polyuria, polydipsia, nausea, or vomiting;
  - Serum ketone level  $> 1.5$  mmol/L or large/moderate urine ketones;
  - Serum bicarbonate  $< 15$  or venous pH  $< 7.24$  or arterial pH  $< 7.3$ ;
  - Treatment provided in a healthcare facility;
- **Risk of loss of confidentiality:** As in any study, there is the potential for loss of confidentiality. Female subjects of childbearing potential will require urine pregnancy testing prior to enrollment in the protocol, and results of this testing have potential to result in loss of confidentiality.
- **Risk of glycemic deterioration:** It is possible that changing dietary requirements or insulin doses may result in glycemic deterioration. Likewise, adolescents may have glycemic deterioration due to non-compliance. During the study, dose adjustments will be made according to standard of care to prevent hypoglycemia and hyperglycemia.
- **Risk of CGM:** Participants have the option of using FDA approved CGM as part of clinical care in our clinics. There is a low risk of developing a local skin infection at the site of the sensor needle placement. Itchiness, redness, mild bleeding, and or bruising may occur at the insertion site. Subjects may develop localized reactions to adhesive used to secure the sensor.
- **Risk of study questionnaires:** Participants may experience some distress when discussing factors important to diabetes, diabetes management, and psychosocial stressors

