## 6.5 Planned Analyses

### 6.5.1 Primary Objective Analysis

- **Statistical Analyses Aim 1:** The unadjusted between-diet-group comparison of the primary endpoint, percent time in the target range of 70-180 mg/dL during the 2nd week of each diet, will be performed using a two-sided paired t-test. The adjusted analysis will be performed using linear mixed effects (LME) modeling, with a random intercept for each subject, diet effect, and adjusting for a participant's age, BMI and duration of diabetes. The mean adjusted between diet-group difference in percent time in the target range will be reported, along with the surrounding 95% confidence intervals based on 500 bootstrapped samples (2.5th percentile and 97.5th percentile of the distribution). Secondary outcomes, including time spent with hypoglycemia (<54 mg/dL, <70 mg/dL) and hyperglycemia (>180 mg/dL, >250 mg/dL), average sensor glucose level, will be analyzed similarly to the primary outcome. The proportion of days with elevated fasting  $\beta$ -hydroxybutyrate levels ( $\geq 0.6$  mmol/L) during each diet period will be compared using paired-proportions z-test in the unadjusted analysis and using generalized linear mixed effects (GLMM) modeling (a random intercept, link=logit for the binary outcome yes/no elevated levels with Bernoulli distribution) with covariates of age, BMI, and duration of diabetes. GLMM will also be utilized in the comparison of the number of episodes of diabetic ketoacidosis and severe hypoglycemic events during each period (a random intercept, link=log for a count outcome with Poisson distribution). Statistical analyses for all aims will be implemented using R and SAS 9.4 (Cary, NC) statistical software. Statistical significance will be established at the two-sided alpha of 0.05.

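### The DKA definition covers only undefined hyperglycemic events, so ketoacidosis without hyperglycemia need not enter the DKA count compared between diets

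*Combined protocol and SAP*

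**What the plan says.** The only DKA definition in the available text is in section 3.2.1, under the risks of ketosis. Its lead-in is "Hyperglycemic events will be classified as diabetic ketoacidosis (DKA) if all of the following are present". Four criteria follow, all of them required:

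- symptoms (polyuria, polydipsia, nausea or vomiting);
- a serum ketone level above 1.5 "mmol/L or large/moderate urine ketones";
- acidosis, by bicarbonate or pH;
- "Treatment provided in a healthcare facility".

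The sentence just before the definition reads "If a participant develops DKA, they will be withdrawn from the study".

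The Synopsis (Aim 1) lists as a safety outcome the "Number of episodes of diabetic ketoacidosis and severe hypoglycemic events during each period". Sections 5.2.1 and 6.2.1 repeat it. Section 6.5.1 states the analysis: "GLMM will also be utilized in the comparison of the number of episodes of diabetic ketoacidosis and severe hypoglycemic events during each period", with a random intercept, log link and Poisson distribution.

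On the diet itself, section 3.2.1 says "Risks of the very low carbohydrate diet include the development of elevated ketone levels". Of earlier low-carbohydrate studies, section 2.2 says "it is likely that the lack of carbohydrate intake led to lower insulin needs, thus increasing lipolysis and ketogenesis". Section 3.1 cites adult observational data in which such diets reduced hyperglycemia, and section 4.1 hypothesises more time in target range on the test diet. Section 6.1.4 marks blinding as not applicable.

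**The concern.** The lead-in makes hyperglycemia the way into the definition, although none of the criteria measures glucose. Glucose is what the diet is meant to change. If classification depends on it, the chance that a given ketoacidosis event is counted may differ between the two diets, even when the event is equally severe.

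The plan says that the test diet raises ketones and expects it to limit hyperglycemia. On those premises, an acidotic event without hyperglycemia is more plausible in the very low carbohydrate period than in the standard one. Leaving such events out could make the test diet look safer in the DKA comparison. Because hyperglycemic event is undefined and assignment is open, whoever classifies a borderline case does so with discretion and with knowledge of the diet.

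The count matters to the trial's purpose. Section 2.2 says that earlier studies of low carbohydrate diets did not specifically monitor for ketosis, and section 3.2 says that this trial will inform safety considerations and dietary recommendations.

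**Working it through.** The plan states no figure for this point, so there is none to reproduce. The check is a comparison of passages, followed by an illustration of scale.

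**1. Is there a glucose condition?** The four criteria cover symptoms, ketones, acidosis and place of treatment. None is a glucose value. The only reference to glucose is the adjective in the lead-in.

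**2. Is that condition defined elsewhere?** The only hyperglycemia cut-offs are the CGM bands above 180 and above 250 mg/dL (Synopsis; section 5.2.1). They are glycemic outcomes and are not linked to the DKA definition. The available text nowhere mentions ketoacidosis at normal or near-normal glucose.

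**3. Can all four criteria be met without hyperglycemia?** As written, yes. Nausea or vomiting alone satisfies the symptom criterion, and section 3.2.1 lists both as possible effects of switching to the diet. The other three criteria do not refer to glucose.

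**4. Do the plan's premises link the condition to diet?**

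| Element | Source | Bearing on the test diet |
|---|---|---|
| Ketones | 2.2, 3.2.1 | expected to rise |
| Hyperglycemia | 3.1, 4.1 | expected to fall |
| Insulin when the diet starts | 6.3.5, Visits 2 and 4 | reduced by 10-20%, as clinically indicated |
| Blinding | 6.1.4 | none |

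**5. What would still record the event?** These routes do not depend on glucose:

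- daily fasting ketone tests, and tests for symptoms (6.2.2);
- the instruction to call for ketones above 1 mmol/L or for symptoms (3.2.1);
- the outcome of days with fasting beta-hydroxybutyrate of at least 0.6 mmol/L (Synopsis; 6.5.1);
- adverse event questions at follow-up visits (6.3.6);
- hospitalization as a seriousness criterion (6.2.3);
- the investigator's review of adverse events as each participant finishes (7.12).

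None of them puts the event into the DKA count. The 0.6 mmol/L outcome measures ketosis, not acidosis.

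**6. Scale, as an illustration.** Assume one participant has one event on the test diet that meets the four criteria without hyperglycemia. Inputs are 20 enrolled (5.4) and 16 remaining after 20% attrition (6.4.2). Exact (Clopper-Pearson) 95% limits for x of n are the 0.025 quantile of Beta(x, n − x + 1), taken as 0 when x = 0, and the 0.975 quantile of Beta(x + 1, n − x). For x = 0 the upper limit reduces to 1 − 0.025^(1/n).

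| n | Event left out | Event counted |
|---|---|---|
| 20 | 0/20: 0 to 1 − 0.025^(1/20) = 16.8% | 1/20 = 5%: 0.1 to 24.9% |
| 16 | 0/16: 0 to 1 − 0.025^(1/16) = 20.6% | 1/16 = 6.25%: 0.2 to 30.2% |

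Exposure per diet is short: 20 × 14 / 365.25 = 0.77 person-years.

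**The case against.** The strongest reply is that the lead-in is ambiguous rather than exclusionary. It says that hyperglycemic events meeting the criteria are DKA. It does not say that only those are, and it is silent on others. The term has no threshold, the working criteria contain no glucose value, and the definition sits under ketosis risks, where the trigger for calling the team is ketones or symptoms. An assessor could count every event that meets the four criteria. This stands, and it is why the point is that such an event *need not* be counted. A reader might infer that the protocol firmly excludes it; the text does not go that far. An outcome definition that permits both readings still needs settling.

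A second reply is that the trial would not miss the event. This also largely stands. Meeting all four criteria means having been treated in a healthcare facility, so the event should surface as an adverse event, and as a serious one if the participant was hospitalized. A reader might infer that ketoacidosis would go unseen; the safeguards in the working argue against that. They do not fix its label in the DKA analysis.

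Third, a reader might infer that the comparison is biased towards the test diet. The documents do not show this. Section 6.4.2 expects 57.5-62.5% time in range on the test diet, which leaves 100 − 62.5 = 37.5% to 100 − 57.5 = 42.5% of time outside 70-180 mg/dL, not split into high and low. Section 3.2.1 also allows that changes of diet or insulin may worsen glycemia. Average glucose does not tell us glucose during an acidotic event, and no frequency of ketoacidosis without hyperglycemia is given for either diet. The direction is a reasonable inference from the plan's premises and no more.

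Fourth, intervals for a proportion of participants are not the planned analysis of episode counts, and the single event is hypothetical. Both are true; the figures show scale only.

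**Conclusion.** The concern holds in a limited form. The plan's one DKA definition is tied to an undefined glucose condition, so an event that meets every listed criterion without hyperglycemia can be left out of a safety count compared between diets. Any omission could fall more on the very low carbohydrate diet and favour it. That rests on the plan's own expectations about ketones and hyperglycemia, together with open assignment; neither the frequency of such events nor the direction of bias is established.

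What is at risk is the event's place in the DKA count and its mixed-model comparison, not its detection. With 16 to 20 participants, and assuming one such event, the DKA statement would change from none observed to one observed. The primary outcome and the sample size are unaffected. The point is modest, but it should be corrected because the trial is meant to inform safety advice.

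**What to change.** For the safety outcome, delete the word Hyperglycemic from the lead-in in section 3.2.1, so that every event meeting the four listed criteria counts as DKA. Leave the criteria as they are. Record glucose at the time of each event and report it descriptively, so that readers can see which events occurred without hyperglycemia. State in section 6.5.1 that the DKA count uses this definition.

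The withdrawal sentence stands directly before the definition, so a change to the wording could also change who is withdrawn. The investigator must reconcile the two and state whether withdrawal uses the outcome definition. This review does not say which rule should apply and proposes no threshold.

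The cost is a short amendment with IRB approval (sections 7.2 and 7.13). No visit, assay or sample size changes, and CGM data are already collected.
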